#### Part B - MAD

The first MAD cohort (Cohort 4) will be initiated after the safety review of SAD Cohort 2, a recommendation to proceed by the SMC, and approval from the Sponsor.

Patients in the MAD cohorts will be randomized 2:1 to either ANK-700 or PBO. Patients will be stratified based upon their use of fumarate medications at study entry within the interactive response technology system. A total of 12 patients will be enrolled per dose cohort (ANK-700, n = 8; PBO, n = 4). Patients will arrive at the clinic on the morning of dosing and will be monitored in-clinic for 8 hours after completion of their first infusion for assessment of acute safety and PK blood sample collection. A total of 3 doses (1 dose every 3 days) will be

administered in Part B, a regimen that was effective in animal models of multiple sclerosis (MS). Patients will return to the clinic on D22, D43, and at 3, 6, and 12 months for follow-up. In the event that patients are unable to return to the clinic for protocol-specified visits, alternative methods for safety assessments and data collection may be employed to ensure the safety of the patient where appropriate.

Doses planned for evaluation in Part B include 0.3 mg/kg (Cohort 4) and 1.0 mg/kg (Cohort 5). Both Part B cohorts will employ sentinel dosing to monitor for the acute and subacute safety of multiple doses of ANK-700. In this design, the first 2 patients in a cohort (1 ANK-700 and 1 PBO) will complete all 3 doses and then complete an additional 14 days of safety monitoring (through D22) before dosing can be initiated in any further patients.

Cohort 5 will only commence after review of the safety, tolerability, and available PK data of all the SAD cohorts (Cohorts 1 to 3) and Cohort 4, recommendation by the SMC, and approval by the Sponsor.

Please see Table 2 for the complete schedule of assessments for Part B.

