end of infusion; HBV = hepatitis B virus; HCV = hepatitis C virus;	; min =
minute; MRI = magnetic resonance imaging;	; PE = physical
examination; PK = pharmacokinetics; SAD = single ascending dose.	to disconditi

Table 2: Schedule of Assessments Part B (MAD) COHORT 4 ONLY

Assessments a	sments a Screening Treatment Period Study Period			10.57	Early Term. b					
Study Day	-28 to 0	1 c	4	7	22	43±2	90±7	182±7	365±14	
Screening Assessments	Screening Assessments									
Informed consent	X					9		3	4	
Medical history/demographics	X			3		51				,
Disease history	X							2, 3		
Inclusion/exclusion	X									
ECG	X					0.8 e	203 SI	203 20 207 70	. 15 . 15	e.
HIV, HBV, HCV testing	X									
Clinical Procedures		*				36. Y	34 3	59. 8	37.	
Physical examination d	Xe									X
Pregnancy test	Xf	$X^{f,g}$	$X^{f,g}$	$X^{f,g}$						
Vital signs h	X	Xg			X					
Concomitant medications and procedures	X	X	X	X	X	X	Х	X	X	X
EDSS i	X	Xg			X		X	X	X	
Safety Assessments									l.	M)
Adverse events		X	X	X	X	X	X	X	X	X
Laboratory tests (safety)	X	Xg	Xg	Xg	X					X
MRI i	$\mathbf{X}^{\mathbf{j}}$				$X^k$		$X^1$			
Study Drug Administration						30.	3.		•	
Randomization		X								
ANK-700 or PBO administration		X m,q	X n,q	X o,q						
Additional Blood Samples							•			
PK blood sample		Xº	Xg	$X^p$	X					
ADA samples		Xg			X		X	X	X	X
						US 8	203	203 80		
										5,0
76 <del></del>										

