# Study ANK-700-01 in Relapsing-Remitting Multiple Sclerosis

a All patients should be contacted by site staff 1 day before each study visit for assessment of COVID-19 signs and symptoms.

- b Early termination visit only if patient discontinues within 28 days of dosing.
- c On D1 patients will be observed in the clinic/hospital unit for 8h after completion of IV infusion and followed up with by phone following discharge 24 hours after dosing.
- d Pes will also be conducted on study as clinically indicated.
- e Includes weight at screening only.
- f Pregnancy test at screening must be serum; serum or urine tests are acceptable on D1, D4, and D7 prior to dosing. Screening and dosing day pregnancy tests must be negative before study drug is administered. Additional pregnancy monitoring per local guidelines may be implemented.
- g Samples/measurements taken pre-dose.
- h Vital signs include pulse rate, temperature, and diastolic and systolic blood pressure.
- i In the event of a suspected disease relapse, an unscheduled MRI and EDSS assessment may be performed if deemed clinically necessary.
- j The screening MRI must be performed ≥ 10 days prior to dosing on D1. For re-screening, the MRI only needs to be repeated if the previous assessment has been completed >3 months of scheduled dosing or if a relapse has occurred since last assessment
- k The MRI at D22 may be performed up to 3 days before the D22 visit.
-  The MRI at D90 may be performed within 2 weeks of the scheduled D90 visit.
- m On D1, patients will be observed in the clinic for 8 h after completion of IV infusion.
- n On D4 and D7, patients will be observed for 4 h after completion of IV infusion.
- o On D1, 1 PK sample will be taken pre-dose (≥ 5 min prior to infusion), with all subsequent PK samples taken after the end of infusion (EOI) at the following time points: EOI 0 (+2) min, EOI 7 (±2) min, EOI 15 (±2) min, EOI 30 (±5) min, EOI 1 h (±5 min), EOI 2 h (±5 min), EOI 3 h (±5 min), EOI 4 h (±5 min), EOI 6 h (±5 min) and EOI 8 h (±5 min). PK samples to be taken from the arm that did not receive the infusion. The exact date and time of each sample collection must be recorded for all collected samples.

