#### 4.2. PART B – MULTIPLE ASCENDING DOSE

The first MAD cohort (Cohort 4) will be initiated after the safety review of SAD Cohort 2 (Part A), a recommendation to proceed by the SMC, and approval by the Sponsor.

Patients in the MAD part will be randomized 2:1 to either ANK-700 or PBO. Patients will be stratified based upon their use of fumarate at study entry within the interactive response technology (IRT) system. A total of 12 patients will be enrolled per dose cohort (ANK-700, n = 8; PBO, n = 4). Patients will arrive at the clinic on the morning of dosing and will be monitored in-clinic for 8 hours after completion of their first infusion for assessment of acute safety and PK blood sample collection. A follow up phone call 24 hours after dosing will be performed to ensure the patient did not experience any acute safety events after discharge.

- If patients are experiencing active AE(s) which require clinical monitoring at the end of the clinic/hospital unit monitoring period they should not be discharged and followed up per PI assessment
- If feasible, patients should be advised to have someone stay with them after discharge until 24 hours have elapsed after study drug administration on D1.
- If patients do not live within 1-hour travel time of an emergency medical facility, they should remain in the clinic/hospital unit for the first 24 hours after study drug administration.
- Patients should be instructed not to drive themselves to seek emergency medical treatment at any time during the study.

A total of 3 doses (1 dose every 3 days on D1, D4, and D7) will be administered in Part B, a regimen that was effective in animal models of MS. Patients will return to the clinic on D22, D43±2, and at 3, 6, and 12 months for follow-up.

Study ANK-700-01 in Relapsing-Remitting Multiple Sclerosis

[figure not shown]
Doses planned for evaluation in Part B include 0.3 mg/kg (Cohort 4) and 1.0 mg/kg (Cohort 5). Both Part B cohorts will employ sentinel dosing to monitor for the acute and subacute safety of multiple doses of ANK-700. In this design, the first 2 patients in each cohort (1 ANK-700 and 1 PBO) will complete all 3 doses and complete an additional 14 days of safety monitoring (through D21) before initiating dosing for any subsequent patients. Based upon the expected short half-life (< 7 minutes) of ANK-700, no accumulation is anticipated with multiple doses administered 3 days apart.

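### After the third Part B infusion, no adverse-event review, safety laboratory test or clinic visit is scheduled for 15 days, and the schedule tables tie the 24-hour call to D1 only

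*Protocol*

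**What the plan says.** Protocol Section 4.2 sets the regimen: "A total of 3 doses (1 dose every 3 days on D1, D4, and D7) will be administered in Part B". It then gives the later visits: "Patients will return to the clinic on D22, D43±2, and at 3, 6, and 12 months for follow-up". The synopsis lists the same days.

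Tables 2 and 3 have no column between D7 and D22. AEs are reviewed on D1, D4, D7 and D22. Safety laboratory tests fall on the same days, and footnote g makes the D1, D4 and D7 samples pre-dose. SAP Appendix 1 repeats both tables.

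Observation differs by dose. For the first, "On D1, patients will be observed in the clinic for 8 h after completion of IV infusion". For the other two, "On D4 and D7, patients will be observed for 4 h after completion of IV infusion". Footnote c concerns D1 and adds that patients are "followed up with by phone following discharge 24 hours after dosing". Section 4.2 is looser: "A follow up phone call 24 hours after dosing will be performed" follows a sentence about the first infusion but does not itself name D1. Later in Section 4.2, and in Section 4.7, doses 2 and 3 are given a 4-hour stay and no call is mentioned.

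Two other items fall late in the interval. Footnote a requires site contact the day before each visit about COVID-19 symptoms, which means D21. Footnote k lets the D22 MRI be done up to 3 days early, which means from D19.

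The first two patients in each cohort are sentinels. After their third dose they are watched for a further 14 days before anyone else is dosed. Section 4.2 ends that period on D21; the synopsis gives the same 14 days but ends it on D22. The Part B DLT window is D1 to D22.

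**The concern.** Part B exists to test the three-dose course, yet the dose that completes the course has the longest wait for a scheduled safety check. Under Section 4.6 a DLT is any AE of Grade 3 or above in the window, or a Grade 2 AE not resolving within 14 days. Between the 4-hour stay on D7 and the D22 visit nobody is scheduled to ask the patient about AEs, so symptomatic events reach the site only if the patient volunteers them or recalls them on D22. Onset dates, which decide whether a Grade 2 event has lasted 14 days, rest on the same recall.

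Timing matters because Section 4.9 pauses enrollment on any DLT. Sections 4.2 and 10.7 state no interval between the ten patients who follow each sentinel pair, so a DLT that comes to light late may do so after others have been dosed. The Safety Monitoring Committee's review of Cohort 4 through D22 also feeds the decision to open Cohort 5.

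**Working it through.** No statistical formula applies; the check is day arithmetic on the schedule.

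**The plan's own figure.** Third dose on D7 plus 14 days: 7 + 14 = 21. This reproduces the D21 in Section 4.2. The synopsis end date does not fit its own 14 days, since 22 − 7 = 15.

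**Lag from each infusion to the next scheduled AE review and safety laboratory test** (Tables 1 to 3):

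| Infusion | Day | Next AE review and laboratory test | Lag | Stay after infusion | 24-hour call in the table |
|---|---|---|---|---|---|
| Part A, single dose | D1 | D4 ± 1 | 3 days (2 to 4) | 8 h | Yes |
| Part B, dose 1 | D1 | D4 | 4 − 1 = 3 days | 8 h | Yes |
| Part B, dose 2 | D4 | D7 | 7 − 4 = 3 days | 4 h | No |
| Part B, dose 3 | D7 | D22 | 22 − 7 = 15 days | 4 h | No |

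**Any contact after dose 3.** The COVID-19 call comes at 21 − 7 = 14 days. An MRI at its earliest comes at 19 − 7 = 12 days. Neither is an AE review.

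**Share of the DLT window.** D8 to D21 is 21 − 8 + 1 = 14 days, and 14/22 = 64% of the window has no scheduled AE review or laboratory test.

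**Infusions affected.** Part B has 24 × 3 = 72 infusions, of which 24 are third doses. On ANK-700 the figures are 16 × 3 = 48 and 16.

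**Sentinel period.** D8 to D21 is the whole of the 14 days in Section 4.2. It contains the D21 call and possibly the MRI, but no scheduled AE review or laboratory test. The D22 visit falls one day after it ends.

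**If Section 4.2 is read as a call after every dose.** A call would then fall on D8, leaving 22 − 8 = 14 days to the next AE review. The gap barely changes.

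**With AE calls on D8 and D14 and an AE question on D21.** Successive gaps after D7 are 1, 6, 7 and 1 days, so the longest interval without a scheduled AE enquiry falls from 15 days to 7.

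**The case against.** The sponsor has a fair case. Section 4.2 expects a half-life under 7 minutes and no accumulation. Section 4.7 says immunologically active antigen is undetectable in animals after 7 days, and Section 1.4 reports no significant findings in a 4-week repeat-dose rat study up to 87.5 mg/kg. Single-dose data give cover: the Cohort 4 course totals 3 × 0.3 = 0.9 mg/kg and follows review of the 1.0 mg/kg single dose; the Cohort 5 course totals 3 × 1.0 = 3.0 mg/kg and follows review of the 3.0 mg/kg single dose. Part A has its own interval of 10 to 12 days between the D4 and D15 visits. Patients are told to report all AEs, onset dates are recorded, and unscheduled laboratory tests are allowed.

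These points lower the likely risk. They do not put an AE enquiry into the interval, and a total given once is not the same as a course given in three parts. Section 4.7 also says tolerance induction can be seen as early as 1 week after dosing, which for dose 3 falls inside the gap.

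A reader might infer more than the documents support:

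- That patients have no contact at all for 15 days. Footnote a requires the D21 call, and footnote k allows the MRI from D19.
- That dose 2 shares the gap. The D7 visit brings an AE review and laboratory tests 3 days later.
- That the whole course is followed less closely than its first dose. This is true only of the days just after dosing: D22 carries laboratory tests, vital signs, EDSS, MRI, PK and antibody samples.
- That the primary endpoint rests on a single look. Treatment-emergent AEs are collected to the final follow-up visit.

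**Conclusion.** The point holds, limited to the third dose. For 15 days after D7 the plan schedules no AE review, safety laboratory test or visit, and the only required contact is a COVID-19 symptom call on day 14 of the interval. The other Part B doses and the Part A dose wait about 3 days. The gap covers 14 of the 22 days of the DLT window and the full sentinel period as Section 4.2 defines it.

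The consequence is weaker and later ascertainment of symptomatic DLTs after the full course, which is worth correcting because the correction is cheap. It does not invalidate the safety analysis. The documents give no event rates, so the number of DLTs missed or found late cannot be estimated.

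The conclusion rests on two readings. First, Tables 2 and 3 are complete as to visit days; blacked-out rows could not fill the gap, because there is no column to hold them. Second, the call in Section 4.2 is the D1 call of footnote c; the other reading leaves 14 days instead of 15.

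**What to change.** In Protocol Tables 2 and 3 and SAP Appendix 1:

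- Extend the footnote c call, as an AE call, to D7 (made on D8). A call after D4 is optional, since D7 follows 3 days later.
- Add one AE call at about D14.
- Have the D21 pre-visit call ask about AEs as well as COVID-19 symptoms.

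In the text:

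- Reconcile the Section 4.2 sentence on the 24-hour call with footnote c, stating which doses it covers.
- Reconcile the end of the sentinel period, D21 in Section 4.2 and SAP Section 2.3.2 against D22 in the synopsis.

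The cost is a schedule amendment and two calls for each of 24 patients (2 × 24 = 48), or three with the optional one (3 × 24 = 72). The D21 change adds no call, and none of this needs a visit or a new procedure.

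Calls will not detect a symptom-free laboratory change that comes and goes before D22. A draw at about D10 would match the 3-day lag after the other doses but adds a procedure and still leaves 22 − 10 = 12 days unsampled. It is optional, and the point does not depend on it.

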# Study ANK-700-01 in Relapsing-Remitting Multiple Sclerosis

a All patients should be contacted by site staff 1 day prior to each study visit for assessment of COVID-19 signs and symptoms.

- b Early termination visit only if patient discontinues within 28 days of dosing.
- c On D1 patients will be observed in the clinic/hospital unit for 8h after completion of IV infusion and followed up with by phone following discharge 24 hours after dosing.
- d Additional PEs will also be conducted as clinically indicated.
- e Includes weight at screening only.
- f Pregnancy test at screening must be serum; serum or urine tests are acceptable on Day 1 (D1) prior to dosing. Screening and D1 pregnancy test must be negative before ANK-700 is administered. Additional pregnancy monitoring per local guidelines may be implemented.
- g Samples/measurements to be taken pre-dose.
- h Vital signs include pulse rate, temperature, and diastolic and systolic blood pressure.
- i In the event of a suspected disease relapse, an unscheduled MRI and EDSS assessment may be performed if deemed clinically necessary.
- j The screening MRI must be performed ≥ 10 days prior to dosing on D1. For re-screening, the MRI only needs to be repeated if the previous assessment has been completed >3 months of scheduled dosing or if a relapse has occurred since last assessment.
- k The MRI at D15 may be performed up to 3 days before the D15 Visit.
- One PK sample will be taken pre-dose (≥at least 5 min prior to infusion), with all subsequent PK samples taken after the end-of-infusion (EOI) at the following time points: EOI 0 (+2) min, EOI 7 (±2) min, EOI 15 (±2) min, EOI 30 (±5) min, EOI 1 h (±5 min), EOI 2 h (±5 min), EOI 3 h (±5 min), EOI 4 h (±5 min), EOI 6 h (±5 min), and EOI 8 h (±5 min). PK samples to be taken from the arm that did not receive the infusion. The exact date and time of each sample collection must be recorded for all collected samples.
- m The prepared saline bag and infusion line should be weighed before and after administration. These weights should be recorded using any available scale with a precision to at least one tenth of a gram (0.1 grams). Both weight measurements should be conducted using the same scale to reduce variability.

Abbreviations: ADA = anti-drug antibodies; D=day; Early Term = early terminate	tion; ECG = electrocardiogram;
EDSS = Expanded Disability Status Scale;	t; h = hours; EOI =

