#### **6.2** Pharmacokinetic Assessments

Blood samples will be collected for measurement of ANK-700 as specified in Appendix 1 Table 1 (Part A), Table 2 (Part B, Cohort 4) and Table 3 (Part B, Cohort 5). The timing of sampling may be altered based on the emerging PK data. The adjustment of the PK sampling schedule is not considered to be a substantial amendment so long as the total number of plasma PK samples and the total blood volume to be collected from each participant will not change. Any adjusted sampling time points will be documented appropriately.

PK parameters of ANK-700 will be determined from the plasma concentration-time data. Parameters will be calculated by non-compartmental modeling methods, using actual elapsed time from start of infusion based on the actual mg administered. The parameters that will be calculated are defined in the table below and will be calculated for single or multiple dosing of ANK-700, as appropriate. Not all listed parameters may be calculable for every patient, and additional parameters may be calculated, if needed, to fully characterize the available data. PK parameters and concentration data will be summarized by Part, by Dose, and by Day (Single dose Day 1, Multiple dose Day 1, Multiple dose Day 4, Multiple dose Day 7, Single and Multiple Dose Day 1 for common doses.

Table 1 Pharmacokinetic Parameters for Part A and Part B After Each Dose

Parameter	Definition	Method of Determination
C max	Maximum observed plasma concentration	Obtained directly from the concentration-time data
T max	Time to first occurrence of $C_{max}$	Obtained directly from the concentration-time data

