$\lambda_{\rm z}$	Terminal elimination rate constant	Terminal phase rate constant calculated by linear regression of the log-linear concentration-time curve. Only those data points judged to describe the terminal log-linear decline will be used in the regression. A minimum number of three data points in the terminal phase will be used in calculating $\lambda_z$ with the line of regression starting at any post- $C_{max}$ data point ( $C_{max}$ should not be part of the regression slope) and including $C_{last}$ , $t_{last}$ . The adjusted correlation coefficient ( $R^2$ adjusted) in general should be greater than 0.90. Any value less than 0.90 may be used at the PK Scientist's best knowledge and judgment. An appropriate number of decimal places should be used for $\lambda_z$ to enable the reported value of $t_{1/2}$ to be calculated.
t 1/2	Terminal elimination half-life	$Log_e(2)/\lambda_z$
AUC last	Area under the plasma concentration-time curve from time 0 to the last measurable time point	The linear-log trapezoidal method will be employed to calculate AUCs. The linear method will be used for all incremental trapezoids arising from increasing concentrations and the logarithmic trapezoidal method will be used for those arising from decreasing concentrations. $AUC_t = \int_0^t \mathbf{C}(\mathbf{t}) d\mathbf{t}.$
AUC inf	AUC from time zero extrapolated to infinity	$AUC_{inf} = \int_0^t \mathbf{C}(\mathbf{t}) d\mathbf{t} + \int_{\mathbf{t}}^{\infty} \mathbf{C}(\mathbf{t}) d\mathbf{t} =$ $AUC_t + C_t / \lambda_{z_m} \text{ where } C_t \text{ is last observed quantifiable}$
		concentration.
%AUC ex	Percentage of AUC (0-inf) obtained by extrapolation	$(1 - [AUC_t/AUC_{inf}]) \times 100$
CL	Clearance	dose/AUC inf
V z	Volume of distribution during terminal phase	$CL/F/\lambda_z$
R acc ,AUC	Accumulation ratio based on AUC	
$R_{acc}, C_{max}$	Accumulation ratio based on Cmax	
$C_{trough}$	Predose plasma concentration	

For cohort by cohort PK analysis, not all PK parameters may be calculated, and non-compartmental analysis may be done using nominal times from start of infusion.

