#### 8.10.1 Pharmacokinetic Concentration Tables, Figures, and Listings

For Part A (SAD) and Part B (MAD), separately, plasma concentrations for ANK-700 will be summarized by treatment group, day of dose, and nominal protocol time point for PKAS. Additionally, Part A and B will be pooled for a combined summary concentration table by dose on the first (Day 1) dose only for PKAS.

A by-subject listing for plasma concentration data for ANK-700, will be listed by study part, treatment group, patient, and day/time of dose for PKAS. Listings will include nominal and protocol time, actual sampling time relative to start of infusion, actual infusion duration, scheduled infusion duration (30 minutes), and difference between scheduled and actual infusion duration.

All individual as well as summary concentration data (mean, SD, minimum, median, maximum, and geometric mean) will be reported in Table, Figures, and Listings to the same precision as the data provided by the Bioanalytical Lab, e.g, if concentrations are provided as 3 significant digits, TFLs will also report individual and summary concentration data as 3 significant digits. N will represent number of subjects in the treatment group, n will represent number of concentrations available at a nominal time, n(blq) will represent number of concentrations available at a nominal time that are blq, and n (ND) will represent number of concentrations available at a nominal time that were not drawn, not analyzed, or analyzed but not reportable. N and n's will be reported as whole number. Pharmacokinetic Parameters Tables, Figures, and Listings

Following figures will be presented for Part A and B, separately, and for Day 1 combined parts A and B (except for individual separate plots for each patient):

- Linear mean (+/- SD) plasma concentration-time profiles for ANK-700 (all doses on one plot)
- Semilogarithmic mean (+/- SD) plasma concentration-time profiles for ANK-700 (all doses on one plot)
- Linear individual concentration-time profiles for ANK-700 (all patients on same dose on one plot)
- Semilogarithmic individual concentration-time profiles for ANK-700 (all patients on same dose on one plot)
- Linear individual concentration-time profiles for ANK-700 (separate plot for each patient)
- Semilogarithmic individual concentration-time profiles for ANK-700 (separate plot for each patient)

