#### 8.10.2 Pharmacokinetic Parameters Tables, Figures, and Listings

For Part A and Part B separately, and Part A and Part B, Day 1 (combined), summary tables of ANK-700 calculable pharmacokinetic parameters will be provided that were calculated using concentrations available in PKAS.

A by-subject listing for PK parameters for ANK-700 will be listed by study part, by treatment group, by patient and day of dose using the PKAS.

Following rules will be followed for reporting PK parameters:

For tmax, only median, minimum and maximum values will be presented.

For all other parameters N, n, mean, SD, CV%, median, minimum, maximum, geometric mean, and geometric CV% will be presented. N will represent the number of subjects in the treatment group and n will represent calculable PK parameter in the treatment group.

Lambda z dependent PK parameters, i.e.  $\lambda z$ ,  $AUC_{inf}$ , CL, Vz will not be summarized if  $r^2$ adjusted is <0.90, and/or span of the terminal phase is <1.3 times the half-life and/or the %extrapolation to calculate  $AUC_{inf}$  is >30%, unless otherwise determined by the PK scientist. Such parameters will be flagged in parameters listing, and if flagged parameters are not used for calculation of descriptive summaries, it will be footnoted in the PK parameters listing. For summarizing or calculating the summary PK parameters, the individual parameter values as provided by the Phoenix software will be used without any truncation.

In tables, figures, and listings, individual and summary  $C_{max}$  will be reported to the same precision as that provided by the Bioanalytical Lab,  $T_{max}$  will be reported in 3 decimal places in hours and all other PK parameters will be reported as 3 significant figures. N and n will be reported as whole number and CV% will be reported in 2 decimal places.

Box plots for  $C_{max}$ ,  $AUC_{last}$ , and  $AUC_{inf}$  and corresponding dose normalized parameters will be created to visually assess dose proportionality.

[figure not shown]

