#### 10.3 Concentrations Below the Limit of Quantification (BLQ)

For PK data, all concentrations BLQ will be labeled as "BLQ" in the concentration data listings. Values that are BLQ will be substituted by for the calculation of descriptive statistics of concentration tables and for the individual and mean concentration-time plots.

For non-compartmental PK analysis, all below the limit of quantification (BLQ) values predose to the first dose, and prior to the first quantifiable concentration will be substituted by zeros. BLQ values between non-BLQ concentrations will be considered missing before the calculation of the PK variables. Terminal BLQ values will be considered missing.

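### No PK sample falls inside the 30-minute infusion, so with a half-life near 7 minutes AUCinf comes out about 21% low and, where calculable, CL and Vz about 26% high

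*Protocol*

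**What the plan says.** Protocol Table 2 (footnote o) has one pre-dose sample on D1, "with all subsequent PK samples taken after the end of infusion (EOI) at the following time points": 0 (+2), 7, 15 and 30 minutes, then 1, 2, 3, 4, 6 and 8 hours. Table 3 says the same for Cohort 5. Table 1 says it for Part A: "subsequent PK samples taken after the end-of-infusion (EOI) at the following time points: EOI 0 (+2) min". The D7 profile in Part B follows the same pattern and stops at 4 hours. Protocol 10.2 and SAP 2.4 give an infusion of about 30 minutes.

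SAP 6.2 runs the noncompartmental analysis "using actual elapsed time from start of infusion based on the actual mg administered". For AUC, "The linear method will be used for all incremental trapezoids arising from increasing concentrations", with the log rule for falling ones. Under SAP 10.3, BLQ values "prior to the first quantifiable concentration will be substituted by zeros". CL is dose divided by AUCinf, and Vz follows from CL and λz. λz needs at least three points after Cmax.

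On the half-life, Protocol 4.2 says, and SAP 2.3.2 repeats: "Based upon the expected short half-life (< 7 minutes) of ANK-700, no accumulation is anticipated". Protocol 12.8 and SAP 6.2 allow sampling times to move on emerging PK data if sample number and blood volume stay the same. Protocol 12.8 leaves further noncompartmental detail to a separate PK analysis plan.

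**The concern.** During a constant-rate infusion of a drug with linear kinetics, concentration rises quickly and then flattens. A straight line from zero to the end-of-infusion (EOI) value cuts off the area under that curve. If the half-life is short relative to 30 minutes, most of the exposure lies in the part that is never sampled.

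Plasma concentrations and PK parameters are the only secondary endpoint stated (Protocol 3.2). The error has one direction, so more patients would not average it out, and neither document warns of it. A reader of the report would take the absolute AUC, CL and Vz at face value and could carry them into later work.

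**Working it through.** The documents give no AUC, CL or bias figure, so there is none to reproduce. I applied the SAP's rule to a known curve.

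**Inputs.** Infusion time T = 30 min (Protocol 10.2, SAP 2.4). Half-life 7 min, the upper edge of the expectation. Sampling times from Tables 1–3; AUC, CL and BLQ rules from SAP 6.2 and 10.3. Assumed: constant rate, linear kinetics, one phase unless stated, pre-dose value zero. The assay limit is not given, so I express it as a percentage of C(EOI) and vary it.

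**True area.** Set steady state Css = 1. Then C(t) = 1 − exp(−kt), with k = ln2/7 = 0.09902 per min and C(30) = 0.9487. True AUCinf = T × Css = 30. The infusion limb holds 30 − 0.9487/0.09902 = 20.42, or 68% of it.

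**SAP area.** Triangle 0.5 × 30 × 0.9487 = 14.23. Decline 0.9487/0.09902 = 9.58, which the log rule plus tail recovers exactly. The sum is 23.81, and 23.81/30 gives −20.6%. CL is 30/23.81 = 1.260, or +26.0%. λz is unbiased, so Vz moves with CL.

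**EOI draw 2 min late.** C(32) = 0.778, and 0.5 × 32 × 0.778 + 0.778 × 10.10 = 20.31: AUCinf −32.3%, CL +47.7%.

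**Other half-lives, on-time draw.** SAP/true = (1 − exp(−kT)) × (0.5 + 1/(kT)).

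| Half-life (min) | AUCinf | CL, if calculable |
|---|---|---|
| 5 | −27.1% | +37.2% |
| 7 | −20.6% | +26.0% |
| 10 | −14.2% | +16.5% |
| 15 | −8.4% | +9.2% |
| 30 | −2.9% | +2.9% |

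**When λz can be estimated.** With an on-time EOI draw as Cmax, the third later sample is at EOI + 30 min, where the level is 2^(−30/half-life) of C(EOI). That is 5.1% at 7 min, 1.6% at 5 min, 0.55% at 4 min and 0.1% at 3 min. So three points are lost at 5 min with a 2% assay limit, at 4 min with a 1% limit, and at 3 min even with a 0.1% limit. AUCinf, CL and Vz are then missing, not biased. AUClast is still reported and still low (at 3 min with a 1% limit, −36.1%).

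**Second phase.** With a 7-min phase plus a 60-min phase holding 30% of AUC, the full schedule gives −13.8% (CL +16.0%), or −22.4% for AUCinf with a late EOI draw. With 50% in the slow phase: −9.9% (CL +11.0%).

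**Would the SAP 8.10.2 filters catch it?** No; they look only at the terminal phase. One is "span of the terminal phase is <1.3 times the half-life". At 7 min, samples from 7 to 30 min after EOI span 23/7 = 3.3 half-lives. The tail beyond 30 min is 0.9487 × 0.0513/0.09902 = 0.49, or 2% of 23.81, against the 30% limit.

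**Two samples moved to 5 and 15 min after infusion start.** At 7 min, C(5) = 0.390 and C(15) = 0.774. The limb becomes 0.98 + 5.82 + 12.92 = 19.71, the total 29.29, the bias −2.4% (−7.2% with a late EOI draw). The two-phase case (30% slow) gives −0.8% on time and −4.4% late with no material assay limit, and −2.5% and −6.1% with a 1% limit.

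**Superposition on the planned samples.** For constant-rate infusion and linear kinetics, Css = C(EOI) + C(EOI+T) + C(EOI+2T) + …, for any number of phases. At 7 min: 0.9487 + 0.0487 + 0.0025 + 0.0001 = 1.000, so AUCinf = 30 × 1.000. In noise-free one- and two-phase runs it came within about 1% for assay limits up to 2%. With a 5% limit the two-phase result was −8.0%, against about −22% for the trapezoid.

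**The case against.** **The half-life is an expectation, not a human result.** Protocol 4.7 reports something related but different from animals: clearance from the circulation in under 7 minutes. If that meant about five half-lives (an assumption, 1.4 min each), at most one sample after EOI would be quantifiable at limits of 0.1–5%, and CL and Vz would not be reported. If the human half-life is 30 minutes or more, little bias remains. This stands, and it makes the size conditional.

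**A reader might infer that CL and Vz will be reported too high at every half-life under 7 minutes, and ever more so as it shortens.** The documents do not support that. SAP 6.2 requires three post-Cmax points for λz, and both documents accept that some parameters may not be calculable. Below about 5 minutes the likelier outcome, depending on the assay limit, is a missing value.

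**A reader might also infer that escalation or dose comparisons are undermined.** They are not. Escalation rests on DLT counts, with available PK as supporting data. Under linear kinetics and equal infusion times the proportional error is the same at each dose and day. On-time Cmax and half-life do not use the infusion limb. Unequal durations weaken this somewhat: at 7 min, infusions of 25 and 35 min give −17.2% and −23.6%.

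**The plan may already cover this, and little depends on it.** The PK analysis plan was not available and could handle the infusion limb. Retiming and additional parameters are already allowed. The analysis is descriptive and tests no hypothesis. This limits the weight of the point, but a rule that biases the only secondary endpoint still needs a correction or a warning.

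**The sensitivity estimate is noisier.** With 10% assay error at 7 min, its simulated CV was 9–10% against 7% for the trapezoid, and 14% against 7% with a late EOI draw. At a 15-min half-life with 15% error it was slightly worse overall (RMSE 11.7% against 10.8%). It should therefore supplement the trapezoid and not replace it.

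**Conclusion.** The point holds, with conditions. As planned, the infusion limb is replaced by one straight line. AUClast is biased low at any short half-life. At about 7 minutes, AUCinf is about 21% low and CL and Vz about 26% high in a one-phase model with an on-time EOI draw; a draw 2 minutes late makes this about 32% and 48%, and a 60-minute second phase brings the AUC error down to about 10–14%. CL and Vz are biased high only where λz can be estimated, which is doubtful at about 5 minutes or less.

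This rests on constant-rate infusion, linear kinetics, the documents' expected half-life and an assay limit they do not give. It is worth fixing because it affects the absolute values of a stated endpoint and is cheap to address. It is not a safety issue.

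**What to change.** 1. **Profiles still to be collected.** If emerging PK confirms a short half-life, use the retiming in Protocol 12.8 and SAP 6.2. Move two late samples (for example EOI 3 h and 6 h on D1, EOI 2 h and 3 h on D7) to about 5 and 15 minutes after infusion start, from the arm not being infused, and keep the last sample. Sample number and blood volume do not change.

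2. **Profiles already collected.** On the planned dates this may be all of them: a last visit by 30 September 2023, less 350 days for the earliest final visit (D351), puts the last Part B first dose at about 15 October 2022, before the November 2022 SAP. State in SAP 6.2 that trapezoidal AUC is expected to be low, and CL and Vz high where calculable. Beside the trapezoidal values, report a sensitivity AUCinf = T × [C(EOI) + C(EOI+T) + …] and the CL from it, with T the actual duration; SAP 8.10.1 already lists "actual infusion duration, scheduled infusion duration (30 minutes), and difference between scheduled and actual infusion duration".
   - Interpolate with the SAP's log rule at actual draw times, and extrapolate a late EOI draw back to actual EOI from the first two post-infusion samples.
   - Report it only where at least two post-infusion samples are quantifiable and the infusion ran at a constant rate. Where the tail cannot be estimated, label it a lower bound.
   - A constant-rate infusion model is an alternative if it allows a second phase. A single-exponential formula using C(EOI) and λz is not: with 30% of AUC in a 60-min phase, C(EOI) = 0.752 and 0.752/0.293 = 2.57 times the true value.

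3. **If the PK analysis plan already handles the infusion limb**, cite it in SAP 6.2.

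The cost is one SAP paragraph, one extra column in the PK parameter tables and, if dosing continues, a documented change of sampling times. Late sampling becomes slightly thinner, schedules may differ between cohorts, and the sensitivity estimate adds little if the observed half-life is about 15 minutes or more.
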